TDM	
Was TDM conducted?
 
 • Yes; • No; • Unknown. 
Date of TDM (DD MMM YYYY)
 
Outcome of TDM:
 
 • Treatment modification; • Treatment discontinuation; • None; • Other (specify); 	Post-index period

Category	Variable	Timepoint
Discontinuation of index treatment	
 Unknown. 
Discontinuation of index treatment:
 
 Yes; No; Unknown. 	Post-index period
	Date of discontinuation (DD MMM YYYY)	
	Reason for discontinuation:	
	
 Patient completed planned course of treatment; Lack of response to treatment; AE; Patient decision (unrelated to AEs); Treatment success (resolution of invasive fungal infection); Death (unrelated to therapy); TDM; Drug-drug interaction; Other (specify); Unknown. 	
Switch to a new antifungal drug after discontinuation of index treatment	
Switch to a new antifungal agent after discontinuation:
 
 Yes; No; Unknown. 	Post-index period
	Start date of subsequent antifungal agent (DD MMM YYYY)	
	End date of subsequent antifungal agent (DD MMM YYYY)	
	Type of new antifungal agent:	
	
 Liposomal amphotericin B; Voriconazole; Posaconazole; Caspofungin; Anidulafungin; Micafungin; Other (specify); Unknown. 	
Other subsequent antifungal use after end of index treatment	Type of new antifungal drug:	Post-index period
	
 Liposomal amphotericin B; Voriconazole; Posaconazole; 	

Category	Variable	Timepoint
	
 • Caspofungin; • Anidulafungin; • Other (specify); • Unknown. 	
	Start date of subsequent antifungal agent (DD MMM YYYY)	
	End date of subsequent antifungal agent (DD MMM YYYY)	
Index treatment administered as part of antifungal combination therapy	
Index treatment administered as part of antifungal combination therapy:
 
 • Yes; • No; • Unknown. 
Type of therapy administered in combination with isavuconazole:
 
 • Liposomal amphotericin B; • Voriconazole; • Posaconazole; • Caspofungin; • Anidulafungin; • Micafungin; • Other (specify); • Unknown. 	Index date, post-index period
	Start date of therapy administered in combination with isavuconazole (DD MMM YYYY)	
	End date of therapy administered in combination with isavuconazole (DD MMM YYYY)	

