**Figure 1 Overview of Study Periods and Examples of Eligible Cases**

### 4.2 STUDY PERIODS

[figure not shown]
The index event is defined as the first initiation of isavuconazole treatment for the invasive fungal infection. The index event serves as the point at which (1) a patient

PFIZER CONFIDENTIAL

qualifies for study inclusion, (2) patient follow-up begins, and (3) the patient becomes at risk for experiencing study outcomes. Study periods for data extraction and variable assessment are defined relative to the index event (Figure 1).

- **Eligibility period:** The index date must occur within the eligibility period, which is the timeframe wherein potentially eligible patients are identified for enrolment. *The dates comprising the eligibility period will be October 15, 2015 (date of isavuconazole approval by the EMA in the EU), to June 30, 2019. The end date of the eligibility period ensures that the latest date of isavuconazole initiation will occur at least 6 months before the end of December 2019 (after which point the medical records may contain data related to the COVID-19 pandemic, which is not of interest for this study). This definition will allow for a minimum of 6 months of follow-up from the date of isavuconazole initiation unless the patient dies or is lost to follow-up within this timeframe.*
- **Pre-index period:** *Baseline data on demographics and medical history will be collected based on all available information in medical records before the index event.*
- **Post-index period:** *The timeframe for follow-up data collection will begin one day post-index treatment initiation and end at the earliest of the following: 6 months after post-index treatment discontinuation, death, or loss to follow-up (Figure 1 and Figure 2). Key timepoints of interest for assessment of clinical response and safety will be at 6 weeks, 12 weeks, and 24 weeks after initiation of index treatment (Figure 2).*

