**Table 1      Outcome Definitions**

Variable	Definition	Timepoint
Death	Death as indicated on the medical record abstraction form.	Post-index period
Clinical response	
Clinical success: Resolution or partial resolution of all attributable clinical symptoms and physical findings.
 
Clinical failure: No resolution of any attributable clinical symptoms and physical findings and/or worsening.
 
When medical record documentation is not clear to the abstractor as to which category should be specified, the investigator should review all available medical record documentation to determine classifications. If the investigator determines there is not enough medical record documentation to make the classification, he or she will indicate that the response is 'unknown'. Since clinical response classification is important to the study, participating sites will be selected for participation in the study based on their reporting whether they have enough medical record documentation to classify the response.
	Post-index period
Radiological response	
Radiological success: <math>\geq 50\%</math> improvement from initial assessment or improvement of at least 25% from the initial assessment for the follow-up at 6 weeks (i.e., day 42 [<math>\pm 14</math> days]) or if end of treatment occurred before this time.
 
Radiological failure: Failure to meet success criteria.
	Post-index period

PFIZER CONFIDENTIAL

CT24-WI-GL03-RF03 1.0 *Non-Interventional Statistical Analysis Plan For Secondary Data Collection*  
*Study 16-Sep-2020*  
 Page 11 of 19

Variable	Definition	Timepoint
	When medical record documentation is not clear enough for the abstractor as to which category should be specified, the investigator should review all available medical record documentation to determine classifications. If the investigator determines there is not enough medical record documentation to make the classification, he or she will indicate that the response is 'unknown.' Since radiological response classification is important to the study, participating sites will be selected for participation in the study based on their reporting whether they have enough medical record documentation to classify the response.	

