### 6.3 ANALYSIS OF CLINICAL OUTCOMES

Each clinical outcome will be analyzed using counts and frequencies at weeks 6, 12, and 24, along with other descriptive information about the clinical outcome itself.

Additionally, time-to-event analyses anchored on the index date of isavuconazole initiation will be performed using the KM method. For each clinical outcome, the time-to-event analyses will result in a KM plot with summary statistics, including survival-time quartiles and KM estimates at weeks 6, 12, and 24 with accompanying 95% CIs. All analyses will be performed for invasive aspergillosis patients, mucormycosis patients, and for the total study population. If subgroup analyses are pursued, Cox regression will be employed to derive HRs and accompanying 95% CIs.

For the death outcome, patients will be categorized as dead, alive, or unknown at each timepoint of interest, and primary cause of death will be tabulated (Appendix 1, Analysis Table 5.1). For KM analyses, a documented death will comprise the event, and patients will be censored at the date when they are last known to be alive (Appendix 1, Analysis Figure 1; Appendix 1, Analysis Table 5.2).

For the clinical response outcome, patients will be categorized as having clinical success, having clinical failure, or unknown response at each timepoint of interest will be tabulated (Appendix 1, Analysis Table 6.1). In addition, rates of reactivation of the same infection and rates of new infection will be documented overall and specific to whether these events occurred during isavuconazole treatment. For KM analyses, clinical response will comprise the event, and patients will be censored at the earliest timepoint of any of the following: loss to follow-up, end of study, or death (Appendix 1, Analysis Figure 2; Appendix 1, Analysis Table 6.2).

For radiological response, patients will be categorized as having a success, not having a response, unknown response, or not applicable (for the first assessment) at the relevant timepoints of interest (Appendix 1, Analysis Table 7.1). Additionally, radiological examination type and bodily location of the examination will be tabulated. For KM analyses, radiological response will comprise the event, and patients will be censored at the earliest timepoint of any of the following: loss to follow-up, end of study, or death (Appendix 1, Analysis Figure 3; Appendix 1, Analysis Table 7.2).

PFIZER CONFIDENTIAL

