CT24-WI-GL03-RF03 1.0 *Non-Interventional Statistical Analysis Plan For Secondary Data Collection*  
Study 16-Sep-2020  
Page 15 of 19

For the mycological response outcome, patients will be categorized having the infection eradicated, presumed eradicated, not eradicated (failure), unknown response, or not applicable (for the initial assessment) at relevant timepoints of interest. Additionally, mycological examination type and biomarker categories will be tabulated at post-baseline visits (Appendix 1, Analysis Table 8.1). For KM analyses, mycological response (eradication or presumed eradication) will comprise the event, and patients will be censored at the earliest timepoint of any of the following: loss to follow-up, end of study, or death (Appendix 1, Analysis Figure 4; Appendix 1, Analysis Table 8.2)

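### SAP 6.3 counts first responses documented after a switch to another antifungal, and plans neither a label nor a split to show it

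*SAP*

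**What the plan says.** SAP 6.3 anchors every time-to-event analysis on the date isavuconazole was started. For clinical response: "For KM analyses, clinical response will comprise the event, and patients will be censored at the earliest timepoint of any of the following", and the list is "loss to follow-up, end of study, or death (Appendix 1, Analysis Figure 2; Appendix 1, Analysis Table 6.2". The lists for radiological response ("loss to follow-up, end of study, or death (Appendix 1, Analysis Figure 3; Appendix 1, Analysis Table 7.2") and mycological response ("loss to follow-up, end of study, or death (Appendix 1, Analysis Figure 4; Appendix 1, Analysis Table 8.2") are the same apart from the table and figure references. Neither stopping isavuconazole nor starting another antifungal appears in any of them.

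SAP Table 1 defines clinical success as "Resolution or partial resolution of all attributable clinical symptoms and physical findings", assessed over the post-index period, with no condition on the drug being taken. The radiological definition mentions end of treatment, but only to set which improvement threshold applies. SAP 4.2 lets the post-index period run to the earliest of "6 months after post-index treatment discontinuation, death, or loss to follow-up (Figure 1 and Figure 2".

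The same section of the SAP will report reactivation and new infection overall and "specific to whether these events occurred during isavuconazole treatment". No such split is described for response. Protocol 9.4.2 records "Switch to a new antifungal agent after discontinuation", with the agent and its start date, and lists insufficient response among the reasons for stopping. SAP 6.5 tabulates discontinuation and switching as treatment patterns, not in relation to response.

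**The concern.** The first primary objective (Protocol 8, SAP 2.2) is worded as the clinical outcomes of isavuconazole. Under the planned rule, a patient who does not respond, stops, starts a different antifungal and then improves enters the response curve in the same way as a patient who improved on isavuconazole. Someone reading the week-24 estimate as the effectiveness of isavuconazole would credit the drug with the second patient and with part of the result of later therapy. Nothing in the SAP text tells that reader which quantity is being reported, and no described table shows how many responses came after a switch.

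**Working it through.** **Do post-switch responses fall inside the reported weeks?** Week 24 is 24 × 7 = 168 days after index. Six calendar months are at least 181 days, so even a patient who stops isavuconazole in the first days is followed past week 24 unless death or loss intervenes. The Protocol's additional stop at 31 December 2019 does not change this: from the latest index date, 30 June 2019, it leaves 184 days. Post-switch responses can therefore enter the week 6, 12 and 24 results, not only the tail of the curve.

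**Is there a planned figure to reproduce?** Not for response. The only sizing table (Protocol 9.5, Table 1) concerns day-42 mortality. It reproduces: Wilson widths at 19% are 8.98, 9.96, 12.41 and 14.83 points for N = 292, 237, 152 and 106, against the stated 9.0, 10.0, 12.5 and 15.0. It has no bearing on the response rule.

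**Size of the excess.** Let s be the share of patients who start a new antifungal before any documented response, and r the share of those who later respond. Ignoring death and loss to follow-up:

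excess = (response under the SAP rule) − (response with a switch counted as non-response) = s × r.

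It is zero if no such switcher later responds, and never negative. The documents give neither s nor r. Assumed values:

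| s | r | Excess (points) | Responses in 600 patients |
|---|---|---|---|
| 10% | 25% | 2.5 | 15 |
| 20% | 50% | 10 | 60 |
| 30% | 75% | 22.5 | 135 |

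Only switchers with no earlier response count in s. If 30% of patients switch but half of them had already responded, s is 15%, and at r = 50% the excess is 7.5 points rather than 15.

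**Would censoring at the switch be an adequate repair?** An illustrative weekly model over 24 weeks has an on-drug response hazard of 0.03, a switch hazard of 0.02 among those still without response, and a varying post-switch response hazard:

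- Censoring at switch: 1 − 0.97^24 = 51.9%.
- Switch as non-response: each week 0.97 × 0.98 = 0.9506 of patients remain on drug without response, so the result is 0.03 × (1 − 0.9506^24) / (1 − 0.9506) = 42.7%.

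| Post-switch hazard | SAP rule | Censor at switch | Switch as non-response |
|---|---|---|---|
| 0.015 | 47.8% | 51.9% | 42.7% |
| 0.03 | 51.9% | 51.9% | 42.7% |
| 0.06 | 57.6% | 51.9% | 42.7% |

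Censoring returns 51.9% whatever happens after the switch, and at the lowest post-switch hazard it lies above the SAP rule itself. It assumes that switchers would have gone on to respond like those who stayed on drug, which is implausible when lack of response is one reason for switching. Treating the switch as a competing event avoids that assumption.

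**The case against.** The strongest reply is that the plan contains no error. The study is primarily descriptive and has no comparator. Response after starting isavuconazole, regardless of later therapy, is a coherent quantity, and all-cause mortality is followed past a switch in the same way. This stands. A reader might infer that SAP 6.3 simply overstates effectiveness, but that follows only if the curve is read as response to isavuconazole. The objective's wording invites that reading; the SAP neither adopts nor excludes it.

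A reader might also infer that every switcher is a treatment failure turned into a success. The documents do not support that. Protocol 9.4.2 also lists adverse events, drug interactions, drug-level monitoring and patient choice as reasons for stopping. Patients are also classified as success, failure or unknown at each of weeks 6, 12 and 24, so an early failure stays visible in the earlier table.

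Nor can one say that the report will be unable to separate the two kinds of response. The data allow it, and the Appendix 1 table shells are an embedded file that could not be read here. What can be said is that the SAP text describes no such split.

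Finally, Protocol 9.10 says calendar dates will not be kept in the data set. That is no obstacle, because intervals from index are enough: SAP 6.3 needs days to response, and SAP 6.5 already derives days from initiation to switch.

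**Conclusion.** The point holds as a gap in labelling and in a supplementary analysis. First responses after a switch are counted, the SAP text does not say so, and it does not separate them, although the same section does this for reactivation and new infection. As response after initiation regardless of later therapy, the planned analysis is valid. As response to isavuconazole, it can err only upward, by s × r.

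The 2.5 to 22.5 point range shows how that product behaves under assumed inputs. It is not an estimate for this study, and it ignores death and loss to follow-up. The true excess could be negligible if few patients switch before responding. Censoring at death in the same analysis is a separate matter and is not part of this figure.

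**What to change.** 1. Keep the planned analysis, and state in SAP 6.3 and in the table and figure titles that response is counted regardless of subsequent antifungal therapy.
2. For each of clinical, radiological and mycological response, add a cumulative-incidence analysis in which starting a new antifungal before any documented response is a competing, non-response event. Do not treat it as censoring.
3. Split the week 6, 12 and 24 responses by whether they were first documented before or after the start of a new antifungal.

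Use the start of a new antifungal as the only boundary. An on/off-isavuconazole boundary would discard responses documented at a visit after a completed course with no new drug; Protocol 9.11 expects visit timing to vary by site. Adding stopping for lack of response as a second boundary would leave some patients classified two ways. Build the analysis from intervals since index, not calendar dates.

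The cost is one extra set of tables and curves and a second response figure that may be lower than the planned one. One limit remains: responses during combination antifungal therapy still cannot be attributed to isavuconazole alone.

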7.3. Mucormycosis

The main risk factors for mucormycosis include diabetes mellitus, hematological malignancies, stem cell/organ transplantations, corticosteroid therapy, and neutropenia.² Mucormycosis is usually diagnosed through identification of causative agents by histopathological analysis of tissue specimens, in patients showing symptoms of the infection.¹ However, diagnosis is challenging, and cultures are only occasionally positive. Initial treatment of mucormycosis typically includes surgery to remove infected tissues and antifungal treatment with amphotericin B.¹

The VITAL clinical trial (NCT00634049) was a single-arm, open-label trial, that included an assessment of the efficacy and safety of isavuconazole for treatment of mucormycosis in 37 patients. The primary outcome was independent data review committee-determined overall response (complete or partial response [treatment success] or stable or progressive disease [treatment failure]) at day 42, day 84, and end of treatment. The results demonstrated that by day 42, 11% of patients had a partial response, 43% had stable disease, 3% had disease progression, 8% had missing assessments, and 35% had died.⁷ The efficacy of isavuconazole and amphotericin B was also compared in a matched case-control analysis.⁷ At day 42, all-cause mortality was similar in cases with isavuconazole as the primary treatment and amphotericin B-treated matched controls (weighted all-cause mortality: 33% vs. 41%; $P = 0.595$).⁷

Although the use of some antifungals are restricted in patients with renal impairment, in a pooled analysis of the SECURE and VITAL trials, isavuconazole was reported to be well tolerated in patients with renal impairment.⁸

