9.9. Data Analysis

This study is primarily descriptive in nature. Categorical variables will be reported as counts (n) and frequencies (%). Continuous variables will be reported using mean, standard deviation, median, minimum and maximum, interquartile range, and range. Time to event outcomes will be assessed using the KM method and will be reported as descriptive statistics (eg, median time to event) with 95% CI. Results will be presented for the overall group (both disease types) and separately for invasive aspergillosis and mucormycosis.

The statistical analysis plan (SAP) will provide a detailed description of analytic populations, analyses to be performed, and methods to deal with missing data and censoring.

Depending on the overall sample size, subgroup analyses may be conducted for main study outcomes (eg, by country, by diagnosis).

Detailed methodology for summary and statistical analyses of data collected in this study will be documented in a SAP, which will be dated, filed, and maintained by the sponsor. The SAP may modify the plans outlined in the protocol; any major modifications of primary outcome definitions or their analyses would be reflected in a protocol amendment. The SAP will define all planned analytic populations and subpopulations, including definitions of overall response and AEs of interest. The SAP will further provide a detailed description of analyses to be performed.

Any known deviations from the planned analyses, the reason for such deviations and all alternative/additional statistical analyses that may be performed as well as the final statistical analysis must be described in a revised SAP before completion of data collection.

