9.9.2. Planned Analysis

9.9.2.1. Analysis Plan for Primary Objectives

Mortality/survival rates will be summarized and reported. Clinical, radiological, and mycological response documented in the medical record will be summarized using proportions and counts for each category. Details of radiological and mycological assessments will be reported in a descriptive manner, including the type of assessment and the assessment findings. Definitions of response will be provided in the SAP. Time to response and all-cause mortality will be analyzed using the KM method and quartiles and 95% CIs will be reported.

Descriptive statistics will be used to describe all AEs and SAEs reported during the medical record review. The safety data described will include event type, relationship to isavuconazole treatment (where known), event severity, event seriousness, action taken with isavuconazole treatment and outcome of the event. Definitions of AEs and SAEs will be described in the SAP. Time from index treatment to first AE onset will be summarized.

Key timepoints of interest for assessment of treatment effectiveness, safety and survival outcomes will be at 6 weeks, 12 weeks, and 24 weeks after initiation of index treatment. In the cases that usual care visits do not directly coincide with these timepoints, the time windows for assessment of outcomes will be defined in the SAP.

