## 6 STATISTICAL METHODS AND ANALYSIS

### 6.1 STATISTICAL CONVENTIONS

Categorical variables will be reported as counts and frequencies of nonmissing observations. Continuous variables will be reported using the number of nonmissing observations, mean, standard deviation, median, first quartile, third quartile, minimum value, and maximum value. Time-to-event outcomes will be assessed using the Kaplan-Meier (KM) method and will be reported as descriptive statistics with 95% CIs. Results will be presented for the overall group (both disease types) and separately for invasive aspergillosis and mucormycosis. Additionally, subgroup analyses may be performed. If so, log-rank tests will be reported, and Cox regression will be employed with presentation of hazard ratios (HRs) and 95% CIs.

Unless otherwise specified, the time between two dates of interest (including time-to-event analyses) will be computed as the difference between the two calendar dates (e.g., date 2 – date 1) and expressed in days.

No imputation for missing values will be performed. Criteria for censoring in KM analyses will be described for each time-to-event outcome analyzed.

Example tables and figure descriptions for analyses described in this section (analysis tables and analysis figures) are provided in Appendix 1.

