#### **6.4 ANALYSIS OF SAFETY OUTCOMES**

Descriptive statistics will be used to tabulate the occurrence of AEs at week 6 (Appendix 1, Analysis Table 9.1), week 12 (Appendix 1, Analysis Table 9.2), and week 24 (Appendix 1, Analysis Table 9.3). These tables will be repeated for SAEs (Appendix 1, Analysis Tables 10.1, 10.2, and 10.3, respectively). Additionally, these tables will summarize the occurrence of any AE, number of AEs, isavuconazole-related AEs, whether action was taken with isavuconazole, and the AE outcome.

KM plots for time to onset of the first AE will be generated (Appendix 1, Analysis Figure 5), and summary KM statistics will be tabulated (Appendix 1, Analysis Table 11). For KM analyses, onset of the first AE will comprise the event, and patients will be censored at the earliest timepoint of any of the following: loss to follow-up, end of study, or death.

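### Censoring at death in the Kaplan-Meier analyses of response overstates how many treated patients respond, and can produce a median time to response that fewer than half ever reach

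*SAP*

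**What the plan says.** SAP section 6.3 makes clinical response, radiological response and mycological response the events in three separate KM analyses that start at isavuconazole initiation. The censoring rule is the same for all three. For clinical and radiological response, "patients will be censored at the earliest timepoint of any of the following: loss to follow-up, end of study, or death". For the third outcome, "mycological response (eradication or presumed eradication) will comprise the event, and patients will be censored at the earliest timepoint" of the same three, death included. For each outcome the SAP reports "survival-time quartiles and KM estimates at weeks 6, 12, and 24 with accompanying 95% CIs".

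Protocol section 9.9.2.1 is the source of the method: "Time to response and all-cause mortality will be analyzed using the KM method and quartiles and 95% CIs will be reported". Neither document mentions competing risks or cumulative incidence, and neither says that a setting without death is the intended target.

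SAP section 6.3 also plans counts at weeks 6, 12 and 24. The categories it lists for the response outcomes contain none for patients who have died. SAP section 6.1 adds the convention that "Categorical variables will be reported as counts and frequencies of nonmissing observations".

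SAP section 6.4 uses the same rule for time to first adverse event (AE): "onset of the first AE will comprise the event, and patients will be censored at the earliest timepoint of any of the following", again with death among them.

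**The concern.** KM censoring assumes that a censored patient could still have the event later, at the same rate as those who remain under observation. That is reasonable for a patient lost to follow-up but false for a patient who has died. Censoring deaths passes their probability on to the survivors, as if the dead would have gone on to respond.

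Response belongs to a primary objective (protocol section 8), and mortality in these diseases is high. There is no comparator arm, so the bias cannot cancel in a contrast. For response it flatters isavuconazole. At a given response rate it grows with the share of patients who die before responding, and therefore with follow-up time. The quartiles suffer too: a median time to response can be printed although fewer than half of the patients ever respond.

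For first AE the same rule works against the drug. The effect there is probably smaller, because fatal AEs are recorded as AEs (protocol section 9.4.4) and count as events. It is not quantified here. The AE counts at weeks 6, 12 and 24 are not affected, nor is the KM analysis of all-cause death.

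**Working it through.** **Inputs.** The plan states no expected response rate or time to response, so there is no figure of its own to reproduce on this point.

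- Mucormycosis, VITAL day 42 (protocol section 7.3): "11% of patients had a partial response, 43% had stable disease, 3% had disease progression, 8% had missing assessments, and 35% had died". These sum to 100%. The 11% is a committee-assessed overall response and serves only as a stand-in for the SAP's outcomes.
- Aspergillosis, SECURE day 42 (protocol section 7.2): 19% mortality. The documents give no response rate, so 50% and 30% are **assumed**.
- Only deaths before a first response matter. I take two cases: all deaths precede response, or half do.

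**Day 42, constant hazards.** Let r be the true cumulative response and d the proportion dying before response. The total hazard is H = -ln(1 - r - d), the response part is H_r = H × r/(r + d), and 1-KM = 1 - exp(-H_r).

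Worked case, r = 0.11 and d = 0.35: H = -ln(0.54) = 0.616; H_r = 0.616 × 0.11/0.46 = 0.147; 1-KM = 1 - exp(-0.147) = 13.7%.

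| True response r | Death before response d | 1-KM |
|---|---|---|
| 11% (VITAL) | 35% | 13.7% |
| 11% (VITAL) | 17.5% | 12.1% |
| 50% (assumed) | 19% | 57.2% |
| 50% (assumed) | 9.5% | 53.2% |
| 30% (assumed) | 19% | 33.8% |
| 30% (assumed) | 9.5% | 31.7% |

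The excess runs from 12.1 - 11 = 1.1 points to 57.2 - 50 = 7.2 points. A simulation of 400,000 patients gives the same 13.7% and 57.2%.

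**Bounds without the constant-hazard assumption.** If every death follows the last response, 1-KM = r. If every death precedes the first response, 1-KM = r/(1 - d). With all deaths occurring without response:

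- VITAL figures: 11.0% to 0.11/0.65 = 16.9%.
- Assumed 50% response, 19% mortality: 50.0% to 0.50/0.81 = 61.7%.

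**Median.** Setting 1-KM = 0.50 and solving for r gives the lowest true response at which KM still prints a median: about 44% for d = 19%, 47.0% for d = 9.5% and 38.4% for d = 35%. If all deaths come first the limit is 0.5 × (1 - d), which is 40.5% for d = 19% and 32.5% for d = 35%.

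**Growth to week 24.** With constant daily hazards a (response, **assumed**) and b (death), 1-KM = 1 - exp(-a·t), and the true cumulative incidence is a/(a + b) × [1 - exp(-(a + b)·t)].

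- Aspergillosis-like: b = -ln(0.81)/42 = 0.00502, a = 0.005.
- Mucormycosis-like: b = -ln(0.67)/42 = 0.00954, from the 33% planning mortality in protocol section 9.5; a = 0.010.

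| | Week 6: 1-KM / true | Week 12: 1-KM / true | Week 24: 1-KM / true |
|---|---|---|---|
| Aspergillosis-like | 19% / 17% | 34% / 28% | 57% / 41% |
| Mucormycosis-like | 34% / 29% | 57% / 41% | 81% / 49% |

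In the mucormycosis-like example the KM median is ln 2/0.010, about day 70, when about 38% have responded. In the aspergillosis-like example it is about day 139. In neither does cumulative incidence reach 50% by week 24.

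**The case against.** The best defence concerns weight rather than correctness.

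- **KM is the additional display.** Both documents list counts and proportions first, the study is descriptive, and no decision threshold depends on these curves. That limits the severity. A descriptive figure must still describe the patients who were treated.
- **The SAP never calls 1-KM the share of patients who respond.** True, but readers will take it so, and no other target is declared. A clear label would remove part of the harm, but the quartiles would still mislead.
- **The count tables may be a sound check.** Their layouts are in a spreadsheet attached to SAP Appendix 1 that was not available for this review, and they may have a row for deaths. The body text leaves the matter open. It does not show that the tables are wrong.
- **The size is mostly assumed.** This stands. The only case built on document figures alone gives an excess of 1.1 to 2.7 points, against a Wilson 95% interval of about 4% to 25% around 11% at n = 37. At 19% mortality the false median needs a true response between about 44% and 50%. Above 50% the KM median is merely too early; well below, none is printed. The week-24 figures rest on assumed hazards held constant.
- **Observed deaths may be fewer than in the trials.** Protocol section 10.2 says that where consent is required, eligible patients must be alive at data collection. Such patients contribute no competing deaths. How many sites this affects is unknown, and it introduces a separate survivor bias.

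None of these points makes the censoring rule appropriate.

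**Conclusion.** The concern holds. As written, the plan overstates cumulative response for all three response outcomes whenever a death without response precedes a later response. That direction needs no assumption about hazards.

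The size is illustrative: about 1 to 7 points at day 42 in the scenarios above, and 16 points (57% against 41%) or 32 points (81% against 49%) at week 24 in the two assumed examples. It depends on the true response rate, on the timing of deaths relative to response, and on whether 19% to 35% mortality by day 42 carries over to these sites. A median that fewer than half of patients reach is possible but not certain.

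This should be fixed before the analysis. It does not undermine the mortality analysis.

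**What to change.** - **SAP section 6.3:** for the three response outcomes, replace KM with the cumulative incidence function (Aalen-Johansen). Treat death before response as the competing event and censor only at loss to follow-up or end of study. Report cumulative incidence with 95% CIs at weeks 6, 12 and 24. Give quartiles as the times at which it reaches 25%, 50% and 75%, or as not reached.
- **SAP section 6.4:** make the same change for time to first AE.
- **Response count tables:** state in which category and denominator patients who have died are counted, preferably as a separate row for death before response.
- **Protocol section 9.9.2.1:** amend the sentence that names KM for time to response. It names KM only for response and mortality, so the first-AE change needs no edit there.
- **Keep** KM for all-cause death. Subgroup Cox models for response can stay if labelled as cause-specific.

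The cost is a SAP revision and some reprogramming. A protocol amendment may also be needed, because protocol section 9.9 says that "any major modifications of primary outcome definitions or their analyses would be reflected in a protocol amendment". No new data are required: date of death is already collected (protocol section 9.4.5), and time to death is needed for the mortality analysis anyway. Reported response figures will be somewhat lower.
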